2.2 Secondary Outcomes

The **secondary study endpoints** will include:

- Number of Grade 3(severe) or higher adverse events that occur at or before Weeks 12, 36, and 48

- Number of Grade 2 (moderate) or higher adverse events that occur at or before Weeks 12, 24, 36, and 48
- Number of AE's of special interest (AESI) at Weeks 12, 24, 36, and 48
- Change in modified Rodnan Skin Score (mRSS) at Weeks 12, 24, 36, and 48
- Provisional American College of Rheumatology Combined Response Index in Systemic Sclerosis at Weeks 12 , 24, and 48.

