7.5.1 Adverse Events of Special Interest

Included in the secondary outcome analysis are the adverse events of special interest (AESI). The adverse events of interest include but are not limited to:

Gastrointestinal perforations	Patients presenting with new onset abdominal symptoms should be evaluated promptly for early identification of gastrointestinal perforations and report SAE if event meets criteria.
Herpes Zoster	Though infection Herpes is a separate event of interest for this study.
Malignancy	Solid cancers, lymphoma, and non-melanoma skin cancer.
Serious Infections	Serious infections due to bacterial, mycobacterial, invasive fungal, viral, or other opportunistic pathogens. Examples of these would include: pneumonia, cellulitis, urinary tract infection, and diverticulitis, tuberculosis and other mycobacterial infections, cryptococcosis, esophageal candidiasis, pneumocystosis, multidermatomal, cytomegalovirus, and BK virus.
Lab value abnormalities compared to screening at any time point and confirmed by repeat testing	
 1. Lymphocyte count less than 500 cells/mm³ 2. ANC less than 500 cells/mm³ 3. AST/ALT >3 ULN 4. Hy's law= ALT > 3x ULN + bilirubin > 2x ULN 5. A drop of Hb by >2 gm/dL 6. Hb ≤ 8 gm/dL 7. Increase in LDL or HDL >50% 8. Increase in serum creatinine >50%

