8 STATISTICAL CONSIDERATIONS

This study is a two-center, double-blind, randomized, placebo-controlled phase 1/2 clinical trial in which the safety and tolerability of tofacitinib will be assessed in patients with early dcSSc, preliminary efficacy (activity) will be estimated, and exploratory mechanistic research assessments will be performed. Fifteen subjects will be enrolled into the trial, which involves a 24-week course of 5 mg BID tofacitinib or placebo, followed by a 24-week open-label extension period of 5 mg BID tofacitinib.

This section describes the planned analyses; however, a statistical analysis plan (SAP) will be written that provides detailed descriptions of the analyses to be conducted. The SAP will be finalized prior to unblinding of the data.

Continuous variables will be summarized using descriptive statistics including n, mean, median, standard deviation, range (e.g., minimum and maximum). Qualitative variables will be

summarized using counts and percentages. Summaries will be provided by treatment group and overall. Unless otherwise specified, statistical analyses will be performed using SAS Version 9 or higher. Where appropriate, statistical tests will be conducted at the 0.1 significance level using two-tailed tests and p-values will be reported. Given the study objectives and size of this study, the statistical power of any comparisons is limited and p-values will be interpreted as hypothesis generating and not definitive. No adjustment for multiplicity will be made.

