1.2. Secondary Endpoints

1.2.1. Secondary Endpoint. Analyses of the Primary Endpoint Over Time.

The analyses of the primary endpoint described in sections 1.1.1 and 1.1.2 will be repeated at Weeks 12 to assess the time course of the safety profile as defined by the occurrence of Grade 3 or higher adverse events.

1.2.2. Secondary Endpoint. Analyses of the Adverse Events at the Grade 2 Threshold.

The analyses described in sections 1.1.1, 1.1.2 and 1.2.1 will be repeated for adverse events beginning at or before the time point of interest that are assessed as at least Grade 2 (moderate) severity.

1.2.3. Secondary Endpoint. % of Subjects with Adverse Events of Special Interest (AESI).

The proportion of subjects in the safety population experiencing an AESI will be compared between the two study treatment arms. Comparisons will be made for at least one AESI of any type, as well as for each of the events that are considered to be of special interest individually. Separate analyses will be performed for AESIs that occur at or before Weeks 12 and 24. AESIs are defined to be any one of herpes zoster, malignancy, serious infection, lymphocytes <500cells mm³, ANC <500cells mm³, AST > 3xULN, ALT > 3xULN, Hy's Law criteria met, Hemoglobin drop > 2mg/dL, increase in HDL/LDL ratio > 50%, or an increase in serum creatinine > 50%.

1.2.4. Secondary Endpoint. Change from Baseline in the Modified Rodnan Skin Score (mRSS).

Change from baseline in the mRSS total score will be compared between the two treatment arms to assess skin thickness relative to the initiation of study treatment at the various time points. The analysis will be performed separately at Weeks 12 and 24 on subjects in the modified intent-to-treat (mITT) population (see section 2.1).

1.2.5. Secondary Endpoint. Provisional American College of Rheumatology Combined Response Index in Systemic Sclerosis CRISS will be compared between the two treatment arms separately at Weeks 12 and 24 on subjects in the modified intent-to-treat (mITT) population (see section 2.1).

1.2.6. Secondary Endpoint. % of Responders as Defined by the mRSS.

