# of SAEs		
# of Subjects with SAEs		
# of Subjects		
SAEs per Subject		
% of Subjects with SAEs		

Table 9: TOFA Proportion of Subjects with SAEs by Severity Grade. Safety Population.

System Organ Class Preferred Term	Tofacitinib N=10 n (%) [1]	Placebo N=5 n (%) [1]
Total Events		
Total Subjects With At Least One Event		
Grade 1		
Grade 2		
Grade 3		
Grade 4		
Grade 5		
Grades 3-5		

[1] Percentages are 100*n/N.

The severity grade shown is the greatest grade reported per event for a particular Subject (Grade 1 < Grade 2 < Grade 3 < Grade 4 < Grade 5).

Listing 3: TOFA Listing of SAEs. Safety Population.

Tro	eatment	Subject ID	SAE#	New SAE since (Date of last report)	SAE Brief Description (Verbatim Term)	Treatment Emergent?	SAE Start Date	SAE Stop Date	Days from Start of Study Medication	Severity Grade	Relationshi p to Study Treatment	Outcome	Study Drug Action Taken	Study Drug Stop Date	Study Drug Start Date	

There were no SAEs reported as of the data cutoff date.

Treatment emergent adverse events are AEs that are began after the first dose of study medication.

Note: Double-Blind Treatment is expected to last 24 Weeks (168 Days). Those SAEs that started >= Day 169 are assumed to have occurred during the Open Label phase.

Data cutoff date: DDMMYY

Listing 4: TOFA Listing of Deaths. Safety Population

Treatment	Subject ID	SAE#	New SAE since Aug 4, 2017	SAE Primary Category	SAE Description (Verbatim Term)	Treatment Emergent?	SAE Start Date	SAE Stop Date	Days from Start of Study Medication	Severity Grade	Relationship to Study Treatment	Outcome	Study Drug Action Taken	Treatment Required

Conditional Note: There were no deaths reported as of the data cutoff date.

Treatment emergent adverse events are AEs that began after the first dose of study medication.

Table 10: TOFA Proportion of Subjects with Adverse Events by Primary Category. Safety Population.

Preferred Term	Tofacitinib n (%) [1]	Placebo n (%) [1]

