		Median		

Lab	Time	Status	Tofacitinib N=10	Placebo N=5
		Min, Max		
	Week 24	N		
		Mean(SD)		
		Median		
		Min, Max		
	Week 30	N		
		Mean(SD)		
		Median		
		Min, Max		
	Week 36	N		
		Mean(SD)		
		Median		
		Min, Max		
	Week 48	N		
		Mean(SD)		
		Median		
		Min, Max		
Total Cholesterol	Screening	N		
		Mean(SD)		
		Median		
		Min, Max		

Lab	Time	Status	Tofacitinib N=10	Placebo N=5
	Week 6	N		
		Mean(SD)		
		Median		
		Min, Max		
	Week 30	N		
		Mean(SD)		
		Median		
		Min, Max		
	Week 36	N		
		Mean(SD)		
		Median		
		Min, Max		
HDL	Screening	N		
		Mean(SD)		
		Median		
		Min, Max		
	Week 6	N		
		Mean(SD)		
		Median		
		Min, Max		
	Week 30	N		

Lab	Time	Status	Tofacitinib N=10	Placebo N=5
		Mean(SD)		
		Median		
		Min, Max		
	Week 36	N		
		Mean(SD)		
		Median		
		Min, Max		
LDL	Screening	N		
		Mean(SD)		
		Median		
		Min, Max		
	Week 6	N		
		Mean(SD)		
		Median		
		Min, Max		
	Week 30	N		
		Mean(SD)		
		Median		
		Min, Max		
	Week 36	N		
		Mean(SD)		

Lab	Time	Status	Tofacitinib N=10	Placebo N=5
		Median		
		Min, Max		
Triglycerides	Screening	N		
		Mean(SD)		
		Median		
		Min, Max		
	Week 6	N		
		Mean(SD)		
		Median		
		Min, Max		
	Week 30	N		
		Mean(SD)		
		Median		
		Min, Max		
	Week 36	N		
		Mean(SD)		
		Median		
		Min, Max		

[1] The safety population includes all patients randomized to TOFA who received at least one dose of study medication.

Note: Lipid panel only done at Screening and Weeks 6, 30, and 36. Data cutoff date: DDMMYY

Table 34: TOFA Vital Signs Over Time. Safety Population [1]

Lab	Time	Status	Tofacitinib N=10	Placebo N=5
Temperature(C)	Screening	N		
		Mean(SD)		
		Median		
		Min, Max		
	Baseline	N		
		Mean(SD)		
		Median		
		Min, Max		
	Week 6	N		
		Mean(SD)		
		Median		
		Min, Max		
	Week 12	N		
		Mean(SD)		
		Median		
		Min, Max		
	Week 24	N		
		Mean(SD)		

Lab	Time	Status	Tofacitinib N=10	Placebo N=5
		Median		
		Min, Max		
	Week 30	N		
		Mean(SD)		
		Median		
		Min, Max		
	Week 36	N		
		Mean(SD)		
		Median		
		Min, Max		
	Week 48	N		
		Mean(SD)		
		Median		
		Min, Max		
Respiratory Rate	Screening	N		
		Mean(SD)		
		Median		
		Min, Max		
	Baseline	N		
		Mean(SD)		
		Median		

Lab	Time	Status	Tofacitinib N=10	Placebo N=5
		Min, Max		
	Week 6	N		
		Mean(SD)		
		Median		
		Min, Max		
	Week 12	N		
		Mean(SD)		
		Median		
		Min, Max		
	Week 24	N		
		Mean(SD)		
		Median		
		Min, Max		
	Week 30	N		
		Mean(SD)		
		Median		
		Min, Max		
	Week 36	N		
		Mean(SD)		
		Median		
		Min, Max		

Lab	Time	Status	Tofacitinib N=10	Placebo N=5

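### Lipids are scheduled once on blinded treatment (Week 6) and not at Week 24, so the Week 12 and Week 24 between-arm lipid AESI results rest on the same single draw

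*SAP*

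**What the plan says.** **Draw times.** The lipid row of the Protocol 6.1 schedule is marked at Screening and Weeks 6, 30 and 36. It is empty at Baseline and Weeks 12, 24 and 48. The note under SAP Table 33 matches: "Lipid panel only done at Screening and Weeks 6, 30, and 36". Schedule footnote m makes the early-termination visit a copy of Week 24, so it has no lipid panel either.

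**Analyses.** Protocol 2.2 lists "Number of AE's of special interest (AESI) at Weeks 12, 24, 36, and 48" as a secondary endpoint. SAP 1.2.3 compares the arms for any AESI and for each type: "Separate analyses will be performed for AESIs that occur at or before Weeks 12 and 24". Tables 29 and 30 give the lipid row a 90% confidence interval and a Fisher p-value at each time point.

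**Definition.** Protocol 7.5.1 introduces the laboratory AESIs as "Lab value abnormalities compared to screening at any time point and confirmed by repeat testing", and the lipid item is "Increase in LDL or HDL >50" per cent. SAP 1.2.3 has "increase in HDL/LDL ratio > 50" per cent and no repeat-test condition.

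**Switch.** The blinded phase lasts 24 weeks, "followed by a 24-week open-label extension period of 5 mg BID tofacitinib" (Protocol 8). The notes to SAP Listings 3 and 5 treat events starting on or after Day 169 as open label.

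**The concern.** The SAP promises a randomised lipid comparison at two time points, but the schedule supplies data for only one. A reader of Table 30 would take its lipid row as the result of 24 weeks of blinded treatment, when on scheduled samples it describes the first six.

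Lipids are also an exception. Protocol 5.5.1 names them among the laboratory values to monitor, and Protocol 1.2.5 reports dose-related lipid elevations with this drug. Yet the blood count and chemistry panel are drawn at Weeks 6, 12 and 24 under blinding, and lipids only at Week 6.

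At stake are an end-of-phase value for the only controlled lipid comparison in the trial and a pre-switch reference for the placebo subjects who start tofacitinib at Week 24.

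**Working it through.** **1. Post-dose draws by phase (Protocol 6.1 schedule).**

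| Panel | Blinded | Open label |
|---|---|---|
| Lipids | Week 6 (1 draw) | Weeks 30, 36 (2 draws) |
| Blood count, chemistry | Weeks 6, 12, 24 (3 draws) | Weeks 30, 36, 48 (3 draws) |

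The lipid count reproduces the SAP Table 33 note.

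**2. Values available to each analysis.** Visit windows are ±10 days.
- Week 6 draw: 6 × 7 = Day 42, so Day 32 to 52.
- Week 30 draw: 30 × 7 = Day 210, so no earlier than Day 200.
- Analysis cut-offs: Week 12 = Day 84; Week 24 = Day 168.

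Both cut-offs fall after Day 52 and before Day 200. The scheduled lipid values up to Week 12 and up to Week 24 are the same set, Screening and Week 6. The lipid rows of Tables 29 and 30 must then be identical.

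**3. Blinded time after the only draw.** Nominally (24 − 6)/24 = 75%. With the window, 168 − 52 = 116 days to 168 − 32 = 136 days, or 69% to 81% of 168.

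**4. Next scheduled repeat.** It comes 30 − 6 = 24 weeks after the Week 6 draw and 30 − 24 = 6 weeks after the switch. A subject randomised to tofacitinib is rechecked on the same drug. A placebo subject is rechecked on a different treatment.

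**5. Pre-switch reference.** The last scheduled lipid value before the switch is 24 − 6 = 18 weeks old.

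**6. Do the two definitions pick out the same subjects?** Suppose LDL rises by half and HDL is unchanged. LDL is then at the Protocol's threshold, but the HDL/LDL ratio becomes 1/1.5 = 0.67, a fall of one third. With the mean changes in Protocol 1.2.5 (LDL +15%, HDL +10%), the ratio of the means becomes 1.10/1.15 = 0.96, a fall of about 4%. The definitions are not interchangeable. The table shells drop the word for ratio, so their label could be read either way.

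**7. What the test could show.** With 10 versus 5 subjects and no event on placebo, Fisher's two-sided p is 0.1009 for 5/10 on tofacitinib and 0.044 for 6/10. At the 0.10 level it takes at least 6 of 10.

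**The case against.** The strongest reply is that Week 6 is well chosen. Protocol 1.2.5 reports that in the rheumatoid arthritis trials lipid changes were present by one month and then held steady. Week 6 falls just after that, and Week 30 is likewise six weeks after the open-label start. This stands for the mean effect. A reader might infer from the 75% figure that three quarters of the lipid information is lost; the documents do not support that. The figure measures unobserved time. What the plateau argument does not supply is a separate Week 24 result for individual rises above 50%, or evidence from this disease population.

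A reader might also infer that the randomised comparison cannot register a lipid AESI at all, because no scheduled repeat falls under blinding. The documents do not support that either. Protocol 6.1 allows unplanned visits, laboratories are local, and a lab monitor reviews values blinded (Protocol 7.8). The SAP definition carries no repeat-test condition, so under the SAP a single Week 6 value would count. What remains is that no text requires or times a repeat, and that the two documents define the event differently.

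Third, the consequence is small. Protocol 8 calls p-values hypothesis generating, and the cited mean rises of 15% and 10% are far from a 50% threshold. That stands and limits the weight of the point. Protocol and SAP also agree on the draw times and the SAP states them openly, so this is a design weakness and not a contradiction.

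**Conclusion.** The concern holds within limits. On scheduled samples, the Week 12 and Week 24 lipid AESI comparisons are one analysis reported twice, the Week 24 row contains nothing after Week 6, and there is no lipid value just before the switch. An unscheduled draw in the blinded phase could change any of these, but the plan does not require one.

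The effect is confined to one component of a secondary safety endpoint. The primary endpoint and its stated power do not depend on it. The lipid definitions need reconciling whatever the draw times: as the SAP words it, a rise in LDL alone lowers the ratio and would not be counted, however many samples are taken.

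**What to change.** **Schedule.** Keep Weeks 6, 30 and 36, and add the lipid panel to the blood already drawn at Week 24, before the first open-label dose. Footnote m then carries it to early termination. Moving the Week 36 draw to Week 24 might look cheaper, but it would break the Week 30/36 pair, the only two scheduled draws close together on open-label drug.

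**SAP.**
- Compute the Week 24 lipid AESI from blinded-phase values only, bounded by the date of the first open-label dose. A fixed Day 169 rule would misclassify some draws, because the Week 24 window runs to 168 + 10 = Day 178.
- Add a Week 24 row to the lipid sections of Table 33 and amend its note.
- Flag early-termination values by days since last dose, since Protocol 4.8 places that visit 30 days after dosing ends.

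**Definitions.** Reconcile Protocol 7.5.1 with SAP 1.2.3 and Tables 12 and 29 to 32, both on LDL or HDL versus the ratio and on whether a repeat test is required.

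**If the Week 24 visits have already taken place,** the SAP and definition changes still apply, and Tables 29 and 30 should state that the lipid row rests on the Week 6 draw plus any unscheduled values.

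**Cost.** A 4-hour fast before Week 24 and one inexpensive assay per subject. A rise first seen at Week 24 would still need an unscheduled repeat to be confirmed under blinding, and a Week 6 rise would be rechecked only 18 weeks later.

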3.1.3. Efficacy Analyses

Table 36: TOFA Change From Baseline in mRSS Total Score. ITT Population

Status	Tofacitinib N=10	Placebo N= 5
Week 12		
N		

Status	Tofacitinib N=10	Placebo N= 5
Mean(SD)		
Median		
Min, Max		
p-value [2]		
Week 24		
N		
Mean(SD)		
Median		
Min, Max		
p-value [2]		
Week 36		
N		
Mean(SD)		
Median		
Min, Max		
p-value [2]		
Week 48		
N		
Mean(SD)		
Median		
Min, Max		

Status	Tofacitinib N=10	Placebo N= 5
p-value [2]		

- [1] The ITT population includes all patients randomized to TOFA.[2] Two-sample t-tests

Data cutoff date: DDMMYY

Table 37: TOFA Responder Status Relative to Baseline in mRSS Total Score. ITT Population [1]

Status	Tofacitinib N=10 n(%)	Placebo N= 5 n(%)	p-value [2]
Week 12			
At least 20% Reduction			
At least 40% Reduction			
At least 60% Reduction			
Week 24			
At least 20% Reduction			
At least 40% Reduction			
At least 60% Reduction			

[1] The ITT population includes all patients randomized to TOFA. [2] Fisher's Exact Test

Data cutoff date: DDMMYY

Table 38: TOFA Change From Baseline in mRSS Scores. ITT Population [1]

Variable [2]	Tofacitinib N=10	Placebo N=5
Week 12		
Total Score		
N		
Mean(SD)		
Median		
Min, Max		
p-value [2]		
Representative Score		
N		
Mean(SD)		
Median		
Min, Max		
p-value [2]		
Maximum Score		
N		
Mean(SD)		
Median		
Min, Max		
p-value		

Variable [2]	Tofacitinib N=10	Placebo N=5
Week 24		
Total Score		
N		
Mean(SD)		
Median		
Min, Max		
p-value		
Representative Score		
N		
Mean(SD)		
Median		
Min, Max		
p-value		
Maximum Score		
N		
Mean(SD)		
Median		
Min, Max		
p-value		

Table 39: TOFA Change From Baseline in Physician Global Health Assessment. ITT Population [1]

Time	Statistic [2]	Tofacitinib N=10	Placebo N=5
Week 12	N		
	Mean(SD)		
	Median		
	Min, Max		
	p-value		
Week 24	N		
	Mean(SD)		
	Median		
	Min, Max		
	p-value		
Week 36	N		
	Mean(SD)		
	Median		
	Min, Max		
	p-value		
Week 48	N		

Time	Statistic [2]	Tofacitinib N=10	Placebo N=5
	Mean(SD)		
	Median		
	Min, Max		
	p-value		

Table 40: TOFA Change From Baseline in Patient Global Health Assessment. ITT Population [1]

Time	Statistic [2]	Tofacitinib N=10	Placebo N=5
Week 12	N		
	Mean(SD)		
	Median		
	Min, Max		
	p-value		
Week 24	N		
	Mean(SD)		
	Median		
	Min, Max		

Time	Statistic [2]	Tofacitinib N=10	Placebo N=5
	p-value		
Week 36	N		
	Mean(SD)		
	Median		
	Min, Max		
	p-value		
Week 48	N		
	Mean(SD)		
	Median		
	Min, Max		
	p-value		

[1] The ITT population includes all patients randomized to TOFA.[2] Two-sample t-testsData cutoff date: DDMMYY

Table 41: TOFA Change From Baseline in Health-Related Quality of Life (HRQOL) using PROMIS-29. ITT Population [1]

Time	Statistic [2]	Tofacitinib N=10	Placebo N=5
Week 12	N		
	Mean(SD)		
	Median		
	Min, Max		
	p-value		
Week 24	N		
	Mean(SD)		
	Median		
	Min, Max		
	p-value		
Week 36	N		
	Mean(SD)		
	Median		
	Min, Max		
	p-value		
Week 48	N		
	Mean(SD)		
	Median		
	Min, Max		

Time	Statistic [2]	Tofacitinib N=10	Placebo N=5
	p-value		

[2] Two-sample t-tests
Data cutoff date: DDMMYY

Table 42: TOFA Change From Baseline in Scleroderma Health assessment Questionnaire-Disability Index (SHAQ-DI). ITT Population [1]

Time	Statistic [2]	Tofacitinib N=10	Placebo N=5
Week 12	N		
	Mean(SD)		
	Median		
	Min, Max		
	p-value		
Week 24	N		
	Mean(SD)		
	Median		
	Min, Max		
	p-value		
Week 36	N		

Time	Statistic [2]	Tofacitinib N=10	Placebo N=5
	Mean(SD)		
	Median		
	Min, Max		
	p-value		
Week 48	N		
	Mean(SD)		
	Median		
	Min, Max		
	p-value		

Table 43: TOFA Change From Baseline in UCLA SCTC Gastrointestinal Symptoms Total Score. ITT Population [1]

Time	Statistic [2]	Tofacitinib N=10	Placebo N=5
Week 12	N		
	Mean(SD)		
	Median		

Time	Statistic [2]	Tofacitinib N=10	Placebo N=5
	Min, Max		
	p-value		
Week 24	N		
	Mean(SD)		
	Median		
	Min, Max		
	p-value		
Week 36	N		
	Mean(SD)		
	Median		
	Min, Max		
	p-value		
Week 48	N		
	Mean(SD)		
	Median		
	Min, Max	_	
	p-value		

^[1] The ITT population includes all patients randomized to TOFA.[2] Two-sample t-testsData cutoff date: DDMMYY

Table 44: TOFA Change From Baseline in Scleroderma-Related Skin Symptoms Assessed by PRO-SRSS. ITT Population [1]

Time	Statistic [2]	Tofacitinib N=10	Placebo N=5
Week 12	N		
	Mean(SD)		
	Median		
	Min, Max		
	p-value		
Week 24	N		
	Mean(SD)		
	Median		
	Min, Max		
	p-value		
Week 36	N		
	Mean(SD)		
	Median		
	Min, Max		
	p-value		
Week 48	N		
	Mean(SD)		
	Median		
	Min, Max		

Time	Statistic [2]	Tofacitinib N=10	Placebo N=5
	p-value		

Table 45: TOFA Change From Screening in PFTs. ITT Population [1]

PFT	Time	Statistic [2]	Tofacitinib N=10	Placebo N=5
% Predicted FVC	Week 12	N		
		Mean(SD)		
		Median		
		Min, Max		
		p-value		
	Week 24	N		
		Mean(SD)		
		Median		
		Min, Max		
		p-value		
	Week 48	N		

PFT	Time	Statistic [2]	Tofacitinib N=10	Placebo N=5
		Mean(SD)		
		Median		
		Min, Max		
		p-value		
% Predicted FEV	Week 12	N		
		Mean(SD)		
		Median		
		Min, Max		
		p-value		
	Week 24	N		
		Mean(SD)		
		Median		
		Min, Max		
		p-value		
	Week 48	N		
		Mean(SD)		
		Median		
		Min, Max		
		p-value		
% Predicted DLCO	Week 12	N		
		Mean(SD)		

PFT	Time	Statistic [2]	Tofacitinib N=10	Placebo N=5
		Median		
		Min, Max		
		p-value		
	Week 24	N		
		Mean(SD)		
		Median		
		Min, Max		
		p-value		
	Week 48	N		
		Mean(SD)		
		Median		
		Min, Max		
		p-value		

[1] The ITT population includes all patients randomized to TOFA.[2] Two-sample t-testsData cutoff date: DDMMYY

Table 46: TOFA Change From Screening to Week 24 in Left Ejection Fraction (Maximum of Range). ITT Population [1]

Time	Statistic	Tofacitinib N=10	Placebo N=5
Week 24	N		
	Mean(SD)		
	Median		
	Min, Max		
	p-value [2]		

Table 47: TOFA Change From Screening to Week 24 in Tricuspid Regurgitation Jet. ITT Population [1]

Time	Statistic	Tofacitinib N=10	Placebo N=5
Week 24	N		
	Mean(SD)		
	Median		
	Min, Max		

Time	Statistic	Tofacitinib N=10	Placebo N=5
	p-value [2]		

[1] The ITT population includes all patients randomized to TOFA.[2] Two-sample t-testsData cutoff date: DDMMYY
